#### 7.5 Withdrawal of Subjects

Study participants may withdraw from the study at any time, with or without reason, and without prejudice to further treatment. The study site Investigator(s) and/or study Sponsor have the right to discontinue study participants. Participants can be discontinued for the following reasons:

- Voluntary withdrawal of consent made by the participant
- A safety concern identified by the Principal Investigator, the Sponsor, or any third party
- Inability of the subject to perform the tasks necessary to provide usable data for the study
- Failure to respond after three documented attempts to contact the subject (lost to follow-up). Potential reasons will be documented.

Once a subject is withdrawn or discontinued they will be required to return the Naída CI M DS sound processor utilized for the study. Subjects who withdraw or who are discontinued from the study will be reported accordingly to the Institutional Review Board. If a subject was discontinued because of a device-related adverse event or serious adverse event

(SAE), the subject must be followed until the adverse event is resolved, the point at which the subject withdraws consent, or the study is concluded.

The Investigator (or authorized delegate) in cooperation with the study monitor will complete a tracking log and/or enter into the Electronic Data Capture system the disposition of each enrolled subject (e.g. completed study, withdrew, discontinued, lost to follow-up). Additional subjects may be enrolled if the minimum sample size cannot be reached due to withdrawn, discontinued or lost to follow-up subjects.

#### 8. Statistics

Data from all subjects meeting inclusion and not meeting exclusion criteria will be combined across all sites for the analysis. No study center will enroll no more than 1/3 of the total subject population for the study. The sample size includes an allowance for dropouts.

The following data will be collected and evaluated as part of this study:

- Chronic speech recognition in quiet (primary efficacy endpoint) for the investigational remote fitting vs. in-office fitting (control).
- Acute speech recognition in quiet for remote fitting vs. in-office fitting (supporting data).
- Subjective feedback (supporting data) about subject reimbursement, subjective outcome measures and remote fitting satisfaction.
- Fitting duration for remote fitting vs. in-office fitting (supporting data).
- Psychophysical data for remote fitting vs. in-office fitting (supporting data).

Descriptive statistics will consist of counts, means, and standard deviations for quantitative variables (primary and supporting outcome measures) and frequency and percent relative frequency for categorical variables.

While baseline variables like age at time of implant, duration of severe-to-profound hearing loss at time of implant, and duration of cochlear implant use at time of enrollment have been shown to be correlated with speech perception results in other studies (Rubinstein et al., 1999; Tyler and Summerfield, 1996), these variables are not expected to affect the outcome of this clinical investigation due to the within-subject design of the study.

The sections below provide a high-level overview, more detailed descriptions will be included in the statistical analysis plan for the study. The statistical analysis plan will be finalized prior to analysis of the data to avoid bias from post-hoc definitions. Deviations from the statistical analysis plan will be documented and included in the clinical study report.

#### 8.1 Sample Size Justification

The primary efficacy endpoint is speech recognition on AzBio in quiet mode for remote fitting (Investigational) vs. in-office fitting (Control). Non-inferiority analyses will be based on paired t-tests looking at the differences in scores calculated using the Investigational speech scores minus the Control speech scores. A one-sided hypothesis test will be used with 0.025  $\alpha$  for the primary efficacy evaluation evaluating the following hypothesis:

$$H_0$$
:  $\mu_{\Delta}$  ≤ -10% versus  $H_1$ :  $\mu_{\Delta}$  > -10%

where  $\mu\Delta$  is the mean of the difference (remote fitting – in-office fitting) on the AzBio sentence test in quiet. A non-inferiority bound of 0.10 (10%) was selected for the AzBio test based on procedures used in previous studies

In addition, during validation of the AzBio sentence test, Spahr and colleagues showed that the 95% confidence intervals for average speech recognition for two-list administration approximated 10%. Based on these observations, performance falling outside of the sample confidence interval or greater than 10% would be considered a clinically significant difference (Spahr et al., 2012). Statistically significant test results that reject the null hypotheses, indicating that the means of the paired differences are greater

than -10 percentage points for AzBio in quiet mode, which will support that the Investigational condition is non-inferior to the Control condition. Previous data supported 6.24% SD for the primary efficacy endpoint. As shown in Table 1 below, with a sample size of 8 complete pairs there is 97% power to rule out a -10% null hypothesis supporting non-inferiority for a one-sided 2.5% test with statistical significance.

Table 1: Paired t-tests to reject the null hypotheses for non-inferiority and superiority

	Non- Inferiority
Test significance level, $\alpha$	0.025
1 or 2 sided test?	1
Null hypothesis mean difference, μο	-10
Alternative mean difference, μ Α	0
Paired SD, σ	6.24
Effect size, $\delta =  \mu_A - \mu_0  / \sigma$	1.603
Power (%)	97
N	8

These calculations are based on the T-distribution non-centrality factor as follows:

$$T_{n,NCF} = \frac{\sqrt{n} \left(\mu_{\Delta} - \mu_{0}\right)}{\sigma}$$

observed based on the non-centrality factor:

Power = 
$$T_{n-1}(T_{n-1}^{-1}(0.975), n-1, \delta = T_{n,NCF})$$

The above sample size calculation provides the minimum sample size for the EO cohort. In addition, 5 ARH subjects will be enrolled in the study to provide confirmatory data for the electric and acoustic fitting mode for subjects wearing an acoustic earhook. The incidence of acoustic earhook use among Advanced Bionics recipients is low, less than 2.5% of US recipients. As such, a confirmatory sample of 5 subjects is considered sufficient in order to provide clinical data via descriptive statistics. Outcomes after remote fitting are expected to be similar between the EO cohort and the ARH group. The total sample size was expanded to 17 (12 EO and 5 ARH) as the expected dropout rate due to withdrawals or lost to follow-up is not expected to exceed 4 subjects. Based on a sample size of 17, the upper bound of the exact event rate was calculated in order to provide complication rates. If no events are observed in 17 subjects, then 16.2% is the upper bound for a one-sided 95% confidence interval on this event rate.

#### 8.2 Data Analyses

Subjects will be analyzed separately for the AzBio in quiet mode for remote fitting (Investigational) and for the in-office fitting (Control) as well as the paired difference. All enrolled subjects that meet the inclusion / exclusion criteria will be included in the intent-to-treat (ITT) population. The analysis will be repeated for the per-protocol (PP) population excluding subjects with major protocol deviations. Protocol deviations will be classified as major if they affect data integrity for the primary endpoint or subject safety as defined in Table 2 below.

Version # 1.2 / Version Date: May 26, 2021

**Table 2: Major Protocol Deviations** 

	Chronic speech perception testing not performed in, at a minimum, a single-walled sound booth.	
	Chronic speech perception testing performed without prior calibration of sound field levels to 74dB SPL.	
	Chronic speech perception testing not performed at 0° azimuth.	
	Chronic speech perception testing not performed at a distance of one meter from the subject.	
Protocol deviations affecting data integrity of	Chronic speech perception testing not performed with speech signals presented at 60 dBA.	
the primary endpoint	Chronic speech perception testing performed without removing hearing devices (if necessary) from contralateral ear for unilaterally implanted subjects.	
	Chronic speech perception testing performed without using foam plugs in contralateral ear for unilaterally implanted subjects with residual hearing in the contralateral ear.	
	Chronic speech perception testing not performed using two lists of AzBio sentences.	
	Chronic speech perception testing not performed bilaterally for bilaterally implanted subjects.	
Protocol deviations affecting subject safety	Protocol deviations that result in a serious adverse event	

#### 8.2.1 Efficacy Endpoints

The primary efficacy endpoint is chronic speech recognition using AzBio sentence tests in quiet for remote fitting vs. in-office fitting. Non-inferiority analysis will be based on a paired t-tests looking at the mean difference in scores (D) calculated from the chronic remote fitting speech perception testing (investigational) minus the chronic in-office fitting speech perception scores. Unilateral and bilateral involvement will be additionally considered in two separate manners for the primary effectiveness analysis endpoint to assess the remote vs local difference. First, the unilateral and the bilateral subjects will be analyzed as separate subgroups. Second, a linear regression analysis for the paired difference will include a covariate for whether the subject is unilateral (reference group) or bilateral in order to evaluate the laterality effect. Clinical significance is defined as ruling out a -10 percentage point difference by rejecting the null hypotheses, indicating that the means of the paired differences are greater than – 10 percentage points, as evidence that the remote fitting is non-inferior to the in-office fitting.

Because the study includes follow-up visits, the possibility exists that some study participants will not complete the entire test protocol. Multiple imputation will be used to analyze the primary efficacy endpoint (SAS PROC MIANALYZE; Little and Rubin [2002]). Subject values will be imputed using observed test scores and selected baseline variables.

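### The 97% power in 8.1 is for a t-test on complete pairs; it does not cover the multiple imputation that 8.2.1 prescribes when scores are missing, and that method's degrees of freedom are not fixed

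*Combined protocol and SAP*

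**What the plan says.** **Sample size (8.1).** "Non-inferiority analyses will be based on paired t-tests looking at the differences in scores", remote minus in-office. On significance level: "A one-sided hypothesis test will be used with 0.025". On the margin: "A non-inferiority bound of 0.10 (10%) was selected for the AzBio test". On variability: "Previous data supported 6.24% SD for the primary efficacy endpoint". Table 1 sets the true difference at 0, and the text concludes that "with a sample size of 8 complete pairs there is 97% power". This is described as the minimum for the EO cohort. The total is then raised to 17 (12 EO and 5 with aidable residual hearing, ARH) because dropout "is not expected to exceed 4 subjects".

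**Analysis (8.2.1).** The paired t-test is named again. Because some participants may not finish, "Multiple imputation will be used to analyze the primary efficacy endpoint", combined with SAS PROC MIANALYZE, using observed test scores and selected baseline variables. The baseline variables, the number of imputations and the df rule are not given. Imputation is not labelled a sensitivity analysis.

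**Who is analysed.** The opening of section 8 combines all eligible subjects, and 8.2 puts all eligible enrolled subjects in the ITT population. Only 8.1 speaks of the EO cohort alone.

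**Related provisions.** Section 7.4.3 exits subjects whose remote fitting cannot be completed for non-technical reasons. Section 7.5 allows extra enrolment if the minimum sample size is not reached. Section 8 defers detail to a statistical analysis plan, to be finalized before the data are analysed.

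**The concern.** Twelve EO subjects less four gives the eight pairs of Table 1. In that situation 8.2.1 does not simply test the eight pairs. It fills in four Visit 3 scores from a model fitted to eight subjects and pools the results, which adds between-imputation variance and changes the reference distribution. The power quoted for the trial then belongs to a different procedure.

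Two further consequences do not depend on the EO-only reading. First, the type I error of the pooled test depends on a df rule that the plan leaves open, and this is a pivotal non-inferiority test. Second, a subject exited because remote fitting failed stays in the ITT population and has no Visit 3 score. Imputing that score from subjects whose fitting succeeded replaces a failure of the investigational method with a success-like result, which favours non-inferiority.

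**Working it through.** **1. The plan's own figure.** Inputs from 8.1: margin -10, true difference 0, paired SD 6.24, one-sided alpha 0.025, n = 8.

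- Effect size = 10 / 6.24 = 1.603.
- Noncentrality = 1.603 × √8 = 4.53, df = 7, critical t = 2.365.
- Power from the noncentral t = 97.1%. The stated 97% is reproduced.
- The same formula gives 99.9% for 12 pairs and 99.95% for 13.

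**2. What imputation changes.** With m imputations, average within-imputation variance W and between-imputation variance B, the pooled variance is T = W + (1 + 1/m)B. Write γ = (1 + 1/m)B / T.

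- Large-sample df: ν_m = (m - 1) / γ².
- Barnard-Rubin df: 1 / (1/ν_m + 1/ν_obs), where ν_obs = [(ν_com + 1)/(ν_com + 3)] × ν_com × (1 - γ) and ν_com = n - 1.

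To illustrate, take γ equal to the fraction missing.

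- *4 of 12 missing:* ν_obs = (12/14) × 11 × (2/3) = 6.3, already below the 7 df of the complete-pair test.
- *1 of 12 missing, m = 50:* large-sample df = 49 × 144 = 7,056, so the critical value is about 1.96. Even complete data on 12 subjects carry only 11 df (critical value 2.201). Using 1.96 on a t with 11 df gives a one-sided error of 3.8%; with 16 df (n = 17) it gives 3.4%. This is why the large-sample rule is too liberal when few scores are missing.

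**3. Simulated power, 12 EO subjects, 4 missing Visit 3 scores.** Difference ~ N(0, 6.24). Assumptions not in the documents: between-subject SD about 10 (values from 5 to 15 were also tried), dropout completely at random, Bayesian normal-regression imputation, m from 5 to 100.

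| Analysis | Power |
|---|---|
| t-test on the 8 observed pairs | about 97% |
| Imputation from Visit 2, with or without one further score, large-sample df | 85-96% |
| Same models, Barnard-Rubin df | 71-88% |
| Intercept-only model, either df rule | 83-98% |
| Four predictors | 44-78% |
| Adding the acute Visit 2 score after remote fitting, large-sample df | 98.5-99.2% |
| Same, Barnard-Rubin df | 94.0-97.1% |

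The last two rows take the acute score as the Visit 3 score plus noise with SD 3.8 (the list variability in 8.2.3), a favourable assumption.

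**4. Fewer dropouts, or pooling.** EO-only, with one to three informative predictors: 87-99% with 3 missing, 95-99% with 2, at least 99% with 1. All 17 pooled with 4 missing: 95-100% in every setting tried.

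**5. Simulated type I error** (true difference -10, nominal 2.5%).

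| Setting | Large-sample df | Barnard-Rubin df |
|---|---|---|
| n = 12, 1-2 missing | about 3-4% | about 1.5-2.3% |
| n = 12, 4 missing | about 2-3% | 0.7-1.8% |
| n = 17, 1-2 missing | about 3% | about 2% |

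The complete-pair t-test stays near 2.5%.

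**The case against.** The strongest reply is that no power loss has been shown for this plan. The models in step 3 are assumed, and 8.2.1 permits others. The plan collects an acute AzBio score immediately after remote fitting, and a model using it can match or beat complete pairs. Four dropouts is a ceiling stated beside the total of 17, not an expectation for EO alone, and 7.5 allows extra enrolment. Nothing in 8.2.1 limits the primary test to EO. Imputation supplements the t-test, and with no missing data the two coincide. A complete-pair primary analysis would also drop non-completers from a plan that declares ITT.

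Most of this stands. A reader might infer that the trial is underpowered, or that 71-96% is what the plan delivers. The documents do not support either: the range depends on choices they do not make, and it applies only to an EO-only test with about 3-4 EO dropouts. A reader might also infer that either the stated power or the stated alpha must be wrong. That is too strong as well, because the excess error arises only under large-sample df, which the plan does not specify, and pooling all 17 removes the power shortfall.

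What the reply does not answer is that 8.1 quotes power for a procedure other than the one 8.2.1 prescribes in the very scenario used to justify 12 EO subjects. Nor does pooling settle the df rule or the handling of failed fittings.

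**Conclusion.** The concern holds as a mismatch and a specification gap. The 97% is correct for 8 complete EO pairs but does not extend to the imputed analysis. In an EO-only test with 4 of 12 Visit 3 scores missing, power is usually below 97%: roughly 71-96% with Visit 2 and at most one further score as predictors, and about 44% to 98% or slightly more across other models. With 0-2 EO dropouts, or with EO and ARH pooled (about 95-100%), there is no material shortfall.

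Two points remain whichever population is used. Large-sample df give about 3-4% one-sided error with 1-2 missing scores at n = 12, and about 3% at n = 17, against 2.5%. And 7.4.3, 8.2 and 8.2.1 read together would impute failed remote fittings from successful ones. The size of that second effect cannot be computed, because the documents give no expected failure rate.

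The simulated figures rest on normal scores, dropout completely at random, and assumed between-subject spread, predictors and number of imputations.

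**What to change.** Choose one of two routes in 8.2.1.

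1. **Imputation stays primary.** State the analysis population (EO, or EO and ARH together). Name the predictors and a large number of imputations. Require Barnard-Rubin df with complete-data df = n - 1. Restate in 8.1 the power for 8 of 12 observed EO pairs under that method.
2. **Observed pairs become primary.** Make the paired t-test that Table 1 powers the primary analysis, and keep imputation as a sensitivity analysis.

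Under either route, state that subjects exited because remote fitting could not be completed are not imputed as ordinary dropouts. Report them as remote-fitting failures, and add a sensitivity analysis that assigns them an unfavourable difference.

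The cost is wording only; no new data or subjects are needed. The downside of route 1 is a less favourable stated power under small-sample df. The downside of route 2 is that non-completers leave the primary test.

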#### 8.2.2 Supporting Data

The following supporting data will also be evaluated using descriptive statistics:

- subjective outcome measures
- custom subject remote fitting satisfaction questionnaire
- custom audiologist remote fitting satisfaction questionnaire
- subject reimbursement questionnaire
- acute speech perception data
- in-office fitting vs remote fitting duration
- psychophysical data
- duration of in-office vs remote fitting.

## 8.2.3 Analyses of Individual Results

A critical difference score will be used to determine whether individual subjects demonstrate a significant decrease in performance between the Investigational (remote fitting) and Control (in-office fitting) conditions. Specifically, the criterion value for the critical difference score will be based upon the test-retest variance on the AzBio test. Gifford (2008) provided a set of data on 35 listeners for the AzBio sentences, wherein two lists of sentences were presented one after the other to cochlear implant recipients. Based on those data, the expected variability between lists has a standard deviation  $\sigma$  of 3.8%. The critical difference score can be computed based on the assumption that (1) the difference scores have a normal distribution, and (2) the difference scores are deemed significant if, under the null hypothesis, the probability of the difference score exceeding the critical score is 1%. Under these assumptions, the critical improvement (or decrement) score CS is equal to:

$$CS = \sigma * b$$

In the above equation, b = 2.33, the percentile of the normal curve corresponding to the desired values of  $\alpha$  = 0.01, one-tailed test. Using Gifford's  $\sigma$  value, the critical difference score for AzBio sentences is 8.9%.

The number and percentage of subjects exceeding, within, and below the critical difference (Investigational - Control) score will be tabulated. The shift will be summarized for both the Experimental and Control results indicating improved, the same, or deteriorated. Further the difference between the two strategies will be evaluated and classified as better for the Experimental strategy, the same for both strategies, or better for the Control strategy. A two-sided exact binomial test will be used to evaluate the null hypothesis that the distribution of subjects showing a performance difference (Investigational is better or Control is better) is distributed equally. This analysis will provide an additional indication of the efficacy of remote fitting relative to in-office fitting based upon individual data.

#### 8.2.4 Safety Endpoint

The safety objective is the absence of unanticipated adverse device effects related to remote fitting.

#### 8.2.5 Supporting Data

Subjective outcome measures, remote fitting acceptability questionnaire data, data from reimbursement questionnaires, acute speech perception data, fitting durations and psychophysiological data will be analyzed descriptively. Descriptive statistics will consist of counts, means, and standard deviations for quantitative variables and frequency and percent relative frequency for categorical variables.

Additionally, subject demographics and study results will be presented descriptively to assess site heterogenity.

#### 9. Adverse Events and Device Deficiencies

An adverse event (AE) is defined as any undesirable clinical occurrence experienced by a study subject when using the HiResolution System or when undergoing research procedures, whether or not the AE is considered to be device-related. The definition of an AE also includes any event related to any study procedures or to any underlying medical condition present at baseline that increases in severity during the study. An underlying medical condition that was present at the time of enrollment will not be reported as an AE, but any increase in severity during the study will be reported as an AE.

All device-related and non-device-related adverse events (AEs) will be tracked and reported accordingly throughout the study as defined above in the investigational plan and in accordance with requirements of an IDE investigation. The AEs will be recorded and tracked between completion of the informed consent form (signed and dated) and two weeks after the participant's last study visit. The number and percent of all subjects experiencing adverse events will be summarized by type, status and frequency of event. Adverse Events will be recorded and will include but are not limited to the following information [refer to Appendix B for Case Report Forms (CRFs)]:

#### 9.1 Adverse Event Definitions and Classifications

#### 9.1.1 Serious Adverse Event

A serious adverse event (SAE) is an event that: a) led to a death, or b) led to a serious deterioration in the health of the subject that:

- resulted in a life-threatening illness or injury,
- resulted in a permanent impairment of a body structure or of a body function,
- required inpatient hospitalization or prolongation of existing hospitalization,
- resulted in medical or surgical intervention to prevent permanent impairment to body structure or a body function, or
- led to fetal distress, fetal death or a congenital abnormality or birth defect.

